The goal of this project is to develop a manual for integrating CC and counseling, which is necessary to ensure standardization across clinicians. Preliminary clinical pilot work has been completed in the TVAMC Telephone Assisted Dementia Outreach (TADO) program. However, the TADO clinical program was not established with the resources or scientific rigor necessary to contribute meaningfully to the scientific literature. Therefore the current protocol is a funded research study that will collect preliminary outcome data to examine the potential efficacy of CC+C.

The impact of this work will be fully realized when an efficacious and highly-accessible collaborative-recovery intervention, such as the one being explored, promotes improved quality of living for community-dwelling veterans and their families rather than resorting to more expensive and undesirable intensive care settings.

8. Potential benefits to the research subject and the knowledge to be gained

The intervention may provide some psychological relief to the participants and their caregivers. Since all participants will be receiving active treatments, this is more likely in this study than in other designs.

Though veterans with dementia who are in the early stages of the disease may be more able to engage in the dyadic intervention, family caregivers of loved ones in the later stages of the disease are equally likely to be distressed and benefit from counseling targets.³² Care consultation interventions and counseling interventions have both been used successfully with heterogeneous dementia diagnoses and severity samples.^{9,12} The primary benefit of a telephone-delivered intervention is increasing access to services for those with limitations on transportation or their ability to attend in-person sessions.

The participants and caregivers may also benefit by gaining a general sense of well-being and satisfaction from the attention that is paid to them during the course of the study. For example, many individuals enjoy discussing their experiences in assessment interviews and through intervention contacts in similar studies.

9. Definition of population to which study is directed and justification

This study involves two groups of participants: 1) the Veteran and 2) their caregiver, selected because they are impacted by a dementia-related disorder. See scope of the problem section above for the justification for conducting an intervention study with this population.

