10. Number of the subjects that will be recruited for study

At least seventy dyads (i.e. 70 veterans and 70 caregivers) will be recruited to achieve a final sample. However, caregivers can participate independently if the veteran is too impaired to participate meaningfully in the study.

11. Subject inclusion/selection criteria

Veterans:

- a. Must be age 19 or older
- b. Must have a diagnosis of dementia or a related disorder
- c. Must live in the community (i.e. not in a VA Community Living Center, nursing home, or other facility)
- d. Must cohabitatem with a caregiver;
- e. Must have reliable access to a telephone
- f. Must be willing to consent to participate or provide assent in conjunction with proxy consent if their decision-making capacity is compromised.

Caregivers:

- a. Must be age 19 or older
- b. Must self-identify as assisting with care for at least 8 hours/week
- c. Must be willing to consent to participate.

The study will include women and minorities and aim to represent the percentage reflected in Tuscaloosa VAMC medical care system (12% women, 44% minorities, and 1% Hispanic origin; though numbers of minorities might be slightly lower in the older cohorts targeted for this study as indicated above). No specific inclusion/exclusion criteria related to race/ethnicity are required.

12. Subject exclusion criteria

In addition to meeting the inclusion criteria outlined above, participants will be excluded in the following cases.

Veterans:

- a. Currently incarcerated
- b. Currently pregnant
- c. Dyads experiencing low levels of distress (as defined by a score of 0 or 1 on the Dementia Services Mini-Screen³², see below)

Note. Baseline or post-assessment interviews will be discontinued for Veterans experiencing severe cognitive impairment that would impair their ability to communicate during an interview, consistent with good clinical practices. However, they will not be excluded from participating in intervention sessions as appropriate and their available data (self-report or proxy report) will be retained for analyses.

Caregivers:

- a. Currently incarcerated
- b. Currently pregnant
- c. Experiencing severe cognitive impairment that would impair their ability to communicate during an interview
- d. Dyads experiencing low levels of distress (as defined by a score of 0 or 1 on the Dementia Services Mini-Screen³², see below)

13. Subject exit criteria

- a. Subjects will exit the study once one of the following conditions are met:

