- b. **Demographics** including: sex, age, primary racial or ethnic group, education, living arrangement, time since diagnosis, years married, number of marriages, number of children, and income adequacy will be collected for the veteran and their caregiver. Income adequacy will be assessed with a single item asking about difficulty paying for the basics, (1 = very difficult to 5 = not very difficult). Individuals will be asked if they have had any previous counseling experience, are taking any antidepressants, anxiolytics, or memory enhancers and whether doses have been stable for the past 3 months.
- c. **Health Literacy** will be measured using a 4-item screener to identify individuals with health literacy issues that could impact their ability to complete self-report measures.
57,58
- d. The **Montreal Cognitive Assessment (MoCA)**³⁵ a 30-point cognitive screening instrument with excellent discriminative power to detect mild cognitive deficits will be used to measure cognitive status.
- e. The **Physical Self-Maintenance (PSM) and Instrumental Activities of Daily Living (IADL) Scale**³⁶ will be used to assess functional status or independence in daily care needs across six physical care domains (i.e., activities of daily living, ADL) and eight IADL domains.
- f. The **Revised Memory and Behavior Problems Checklist (RMBPC)**³⁷ which provides an estimate of the frequency of problems and the impact that these problems have on the caregiver will be used to rate behavioral symptoms of dementia.
- g. The **Cornell Scale for Depression in Dementia (CSDD)**³⁸ which relies on an interview with the individual and the caregiver will be used to assess depressive and anxiety symptoms.

- h. The **Quality of Life in Alzheimer's Disease scale (QOL-AD)** will be used to assess quality of life.³⁹ Patients and caregivers rate thirteen domains: physical health, energy, mood, living situation, memory, family, marriage, friends, chores, fun, money, self and life as a whole, using a Likert-type scale.
- i. The **Euro-QoL-5 Domain (EQ-5D)** mobility, selfcare, and usual activities subscales will be used to assess autonomy and functional dependence.⁴⁰ Health-related quality of life is assessed for five domains: mobility, self-care, usual activities, pain/discomfort and anxiety/depression. Caregivers also complete this measure, as has been done in previous studies with individuals with mild to moderate dementia.^{40,41,42}

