r. The 6-item **Desire to Institutionalize (DTI)** Scale⁵¹, which assesses the caregivers planning, thoughts, and actions about long-term care (LTC) placement over the past 6 months will be used to assess intentions to institutionalize their loved one. Six yes/no items (e.g., taken steps toward placement) are summed for a score of 0-6. Long-term care placement and/or hospitalization of the veteran (institutionalization) will be assessed using a single item rated either by the caregiver or via electronic health record review if the dyad is no longer enrolled in the study (e.g., due to attrition).

s. The 21-item **Care Consultation Satisfaction Survey** will be used to measure the participants' satisfaction with the Care Consultant and the Care Consultation services provided.

Once baseline data are collected, dyads will be randomly assigned to a condition (see interventions delivered below).

Randomization

Blocked randomization stratified by race and gender will be used to assign participants to either the: (a) CC group, or the (b) CC+C group. This two-group experimental design was chosen over other approaches (e.g., no comparison group designs, three-group design, cross-over design, etc.) because it most closely approximates the next level of clinical research (e.g., an efficacy study), which allows for the most directly applicable conclusions.

Interventions Delivered

1. Care Consultation (CC): is an established telephone-based, empowerment intervention that uses coaching and emotional support to mobilize family caregivers and individuals with dementia through psychoeducation, resource referral, psychosocial support, and encouragement of informal and formal service use utilization. A computerized clinical tool utilizing a password-protected VA-hosted website (i.e., operated within the VA server system) called the Care Consultation Information System (CCIS) guides the care consultant through a standardized delivery of protocol components, replacing a paper-based clinicians manual. Rather than a strong focus on assessment, this intervention is designed to quickly identify areas of unmet need through brief trigger questions called the “initial assessment” – much like an interview guide – which then immediately shapes development of concrete action plans.

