Missing values are unavoidable in applied clinical intervention research. Where possible, variables to index the number and reasons for missing values will be documented. Based on the distribution of these missing value indices we may choose to eliminate some participants from the analyses ("list-wise deletion"). The extent that missing values are related to the independent (treatment group) or outcome variables will be assessed and if necessary controlled for statistically. Individuals who complete at least four sessions of the intervention (CC or CC+C) will be included in final analyses when time 2 data are available. Strict intention-to-treat methodologies are too conservative for this relatively small initial pilot study.

Data Analysis:

A series of one-way between subjects analyses of covariance (ANCOVAs) will be used to examine the main effect of “group” on 6 month variables of interest while controlling for values at baseline. The dependent variable in these analyses will be change scores with pre-treatment scores as the covariate. This analysis is statistically equivalent to ANCOVA with pre-treatment scores as the covariate and 6-month scores as the dependent variable, but it has an interpretational advantage in that the change scores represent an individual treatment effect (change during treatment). The change scores also represent the interaction term of a 2 (Group) X 2 (Time) repeated measures ANOVA. Consequently, when other covariates are added to the ANCOVAs to address treatment moderation effects, those covariate effects will be directly interpretable as moderator effects. That is, the added terms will assess the effects of the covariates on changes during treatment irrespective of Group (essentially a Time by Covariate interaction). When the interaction (multiplicative product) of covariate and Group is also added as another term in the ANCOVA, that interaction term will supply the moderating effect of the covariate on change during treatment as function of Group (i.e., differential effect of treatment as a function of the covariate).

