Subjects will be given ample time to read and consider the informed consent. Subjects may have as much time as needed (no time limit) to read and consider the risks and benefits of the study participation. Subjects may involve family members, or significant others in the decision on whether or not to participate in the study. Subjects are informed that refusal to participate in research projects will not change their eligibility for VA services, treatment, or disability payments. No guarantees are made for benefit during the research study. Given this study population, it is anticipated that the consent process will take longer than most participant groups.

29. Resources.

All named investigators and research assistants are currently qualified and are trained and experienced in clinical research. They all have adequate offices and space and adequate access to patient's needed for the study.

30. Safeguards to protect the rights and welfare of mentally disabled and/or decisionally impaired subjects (vulnerable patient populations).

This study sample will include participants with varying degrees of cognitive impairment (from intact to severely impaired) and other mental health diagnoses (e.g., serious mental illness) that would classify them as vulnerable populations. In the event that these participants have impaired decision-making capacity, appropriate surrogate consent will be obtained as described above. All members of the investigative team have previous experience conducting research with individuals with impaired decision-making capacity. In addition, the Data Safety Monitoring Board (DSMB) will convene on a biannual basis to review the progress of the study and evaluate the ongoing safety of participants. If at any time during the course of the study, the DSMB judges that risk to participants outweighs the potential benefits, the DSMB has the discretion and responsibility to recommend that the study be terminated.

31. Plans for Adherence to VA Policies and Regulations Regarding Research Involving Controlled Drugs <N:\HRPP POLICIES\Use of Controlled Substance in Research 102706.TIF>:

Not applicable - Controlled drugs will not be used in this research study.

32. Reuse of data

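### Baseline severity (MoCA, PSM ADL/IADL) is collected but unused in the main ANCOVAs; pre-specifying one severity covariate is a cheap gain in precision

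*Combined protocol and SAP*

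**What the plan says.** Section 30 describes the cognitive range: "This study sample will include participants with varying degrees of cognitive impairment (from intact to severely impaired"). The veteran criterion in section 11 is "Must have a diagnosis of dementia or a related disorder", with no limit on severity.

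Table 1 in section 17 schedules the MoCA (veteran) and the PSM IADL/ADL scale (caregiver) at baseline only. The Measures text calls the MoCA a "30-point cognitive screening instrument with excellent discriminative power to detect mild cognitive deficits will be used to measure cognitive status" and gives it no analysis role. Under Randomization, "Blocked randomization stratified by race and gender will be used to assign participants"; cognition is not a stratum.

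Section 20, Data Analysis, tests group on "6 month variables of interest while controlling for values at baseline". Further covariates enter those models only as moderators, and Aim 3 names two: behavioral symptoms and spousal status. The logistic model for nursing home placement allows relevant covariates but does not name them. A partial eta squared of .01 or more is to be read as possibly of clinical importance.

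**The concern.** Disease severity is an obvious candidate predictor of outcome in a dementia trial. The protocol gives some support: section 8 says veterans in the "early stages of the disease may be more able to engage in the dyadic intervention", and section 7 says that the care situation and distress shift as the disease progresses. If severity predicts 6-month change beyond the outcome's own baseline score, leaving it out costs precision in a sample with little to spare. With about 25 dyads per arm, the arms will also differ somewhat in severity by chance. The unadjusted group effect then includes part of that difference, in the same direction for every outcome that depends on severity. The measures that could deal with this are already being collected.

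**Working it through.** **The plan's own figure.** Section 20 gives 70 dyads recruited for 50 completers, an implied loss of 20/70 = 28.6%. The power analysis is deferred to grant text outside the documents and cannot be reproduced.

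**Inputs.** N = 50 analysed (section 20). Equal allocation, 25 per arm, is assumed because the ratio is not stated. The partial correlation r between severity and the 6-month score, given the baseline score, is not in the documents; 0.1 to 0.5 is shown as an assumption. Effects are in residual SD units of the planned model.

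**The .01 threshold as a difference.** With group and baseline in the model, df = 47. F = (0.01/0.99) × 47 = 0.475, and d = √0.475 × √(4/50) = 0.689 × 0.283 = 0.195.

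**Chance imbalance.** The standard error of the difference in mean severity is √(4/50) = 0.283 SD. So P(|difference| > 0.3 SD) = 29% and P(|difference| > 0.5 SD) = 8%.

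**Shift in the group effect.** Shift = r × imbalance. The imbalance needed to reach the threshold alone is 0.195/r, and its two-sided probability is 2 × [1 − Φ(0.195/(0.283 r))].

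**Precision.** SE ratio (adjusted/unadjusted) ≈ √(1 − r²) × √(47/46). The second factor is the cost of estimating one more coefficient. The equivalent gain in dyads is 1/ratio² − 1.

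| r | Shift at 0.3 SD | Shift at 0.5 SD | Imbalance needed alone | Share of randomizations | SE ratio | Equivalent dyads |
|---|---|---|---|---|---|---|
| 0.1 | 0.03 | 0.05 | 1.95 SD | <0.01% | 1.006 | −1% |
| 0.2 | 0.06 | 0.10 | 0.97 SD | 0.06% | 0.990 | +2% |
| 0.3 | 0.09 | 0.15 | 0.65 SD | 2.2% | 0.964 | +8% |
| 0.4 | 0.12 | 0.20 | 0.49 SD | 8.5% | 0.926 | +17% |
| 0.5 | 0.15 | 0.25 | 0.39 SD | 17% | 0.875 | +30% |

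At r = 0 the ratio is √(47/46) = 1.011. Simulated ANCOVAs with 25 per arm agree with the SE ratios to within 0.002.

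**Imbalance combined with noise.** Suppose there is no true effect and the observed imbalance is D. The chance of crossing the threshold in the direction of the imbalance is about 1 − Φ((0.195 − rD)/(0.283√(1 − r²))). For D = 0.5 and r = 0.3 this is 1 − Φ((0.195 − 0.150)/0.270) = 43%; for r = 0.5 it is 59%. For D = 0.3 the figures are 35% and 43%. With the covariate in the model it is about 25% in each case, which is half of the two-sided rate below.

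**The threshold itself.** With no true effect and averaged over randomizations, P(partial eta squared ≥ .01) is P(F on 1 and 47 df ≥ 0.475) = 49.4% under the planned model. With the covariate it is P(F on 1 and 46 df ≥ 0.465) = 49.9%.

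**The case against.** The planned model is standard and valid. Under randomization, omitting a prognostic covariate does not bias the group estimate on average, and its standard error already allows for chance imbalance. The size of any gain rests wholly on a correlation that the documents do not give; at r = 0.2 it is 1% of the standard error. The section 8 sentence on early-stage engagement goes on to say that caregivers of people in later stages are just as likely to be distressed and to benefit, and the next sentence reports success in samples of mixed severity. Better engagement in early disease would also suggest effect modification, which a main-effect covariate does not address. All of this stands. It limits the point to an improvement, best supported for veteran outcomes.

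A reader might infer that an everyday imbalance is enough to produce a spurious effect at the .01 threshold. The figures do not support that. An imbalance of 0.3 SD, exceeded in 29% of randomizations, shifts the effect by at most 0.15 over the range shown, short of 0.195. An imbalance of 0.5 SD, exceeded in 8%, gets there only at r of about 0.4 or more. A reader might also infer that all of the severity effect sits in the error term; only the part not carried by the baseline score does.

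Nor is severity shut out of every between-arm analysis, since the placement model leaves its covariates open. That wording does not pre-specify severity, however, and does not extend to the ANCOVAs.

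**Conclusion.** The point holds as a low-cost improvement. The main ANCOVAs leave available baseline severity measures unused, at a cost in standard error of about 1% to 12% for r between 0.2 and 0.5. The adjustment would also remove the tilt that an observed imbalance gives to severity-related outcomes. The case is weaker for caregiver outcomes such as burden, where section 8 gives no reason to expect severity to predict change.

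It would be wrong to conclude that adding severity makes the .01 rule safe. Noise crosses that threshold in about half of trials with or without the covariate, so the rule is a separate problem.

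The figures assume 50 analysed dyads, equal allocation, a linear severity effect, and imbalance from randomization only. They do not cover selection through the four-session and time 2 data requirement in section 20.

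**What to change.** In section 20, Data Analysis, pre-specify one baseline severity covariate for each main ANCOVA:

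- **Veteran self-report series:** MoCA.
- **Proxy and caregiver series:** PSM ADL/IADL. It is rated by the caregiver, so it does not depend on the veteran being testable.
- **Missing MoCA:** section 12 says "Baseline or post-assessment interviews will be discontinued for Veterans experiencing severe cognitive impairment", and caregivers may take part alone. Under the list-wise deletion that section 20 allows, a MoCA covariate could drop the most impaired veterans. State in advance what level of missing baseline MoCA counts as material. If it is exceeded, use PSM ADL/IADL for the whole veteran series, and make that decision without reference to outcomes.
- **Reporting:** give the model without the severity covariate as a secondary result.

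The cost is a few lines of analysis text and one degree of freedom per model. If severity proves unrelated to change, the standard error is about 1% larger (0.6% at r = 0.1). No new data are needed.
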